### C. Hypothesis

The hypothesis regarding the scoring is that patients receiving ORIGIN implants will experience a more natural feel of the prosthesis during the first year after the surgery compared to patients receiving VANGUARD implants (as measured with FJS), and slightly significant improvement at the following interval of 2 years. The overall patient satisfaction is expected to be improved after 2 years follow-up. It is also supposed that the overall patient satisfaction is expected to be 13.4 points higher with ORIGIN PS than with VANGUARD PS treatment. (Cf. Chapter Statistical Analysis. Section A. Sample size calculation)

### D. Anticipated adverse events assessment

Adverse effects of the ORIGIN® knee prosthesis are similar to other total knee prostheses on the market.

The expected anticipated adverse events in knee replacement surgery are:

- Displacement and loosening (wear, lysis) of the prosthesis
- Patellar component dislocation, tibial insert component disassociation, femorotibial luxation instability, malalignment, malposition
- Pain, stiffness
- Infection
- Venous thrombosis and pulmonary embolism
- Cardiovascular disorders
- Hematoma
- Delayed wound healing
- Grating sounds in the friction pairs, clicking sensation between post-cam (Tibia Insert plot and Femoral cam), soft tissue impingement, patellar component clunk syndrome
- Implant breakage
- Periprosthetic fracture
- Other effects not known to date or not scientifically established

The list of reportable adverse events in the Adverse Event Form is in explained in the XVI.ADVERSE EVENTS, ADVERSE DEVICE EFFECTS AND DEVICE DEFICIENCIES.

The following list of safety outcomes should be collected in the eCRF case report form which will trigger a notification to Symbios regulatory department via [[contact]](mailto:[contact]):

SYMBIOS		 symbios  Clinical Investigation Plan	F029.03
Date	27.11.2019		Distribution Informatique pdf
Auteur	BGA		
Contrôle	EBO		
Libération	RAQ		

- Serious Adverse Events (SAEs)
- Unanticipated Adverse Device Effects (UADEs)
- Devices deficiencies
- Non-serious Adverse Events related to the device or study procedure
- Secondary surgical procedures or revisions
- Surgical complications

SYMBIOS		 symbios  Clinical Investigation Plan	F029.03
Date	27.11.2019		Distribution Informatique pdf
Auteur	BGA		
Contrôle	EBO		
Libération	RAQ		

## VII. DESIGN OF THE CLINICAL INVESTIGATION PLAN

---

### A. Study description

This is a prospective, comparative, randomized, double arm, monocentric, observational, post-market study. The study is performed in Germany, in the University Medical Center of Johannes Gutenberg-University Mainz (UMC- Mainz).

It is stated that 140 subjects implanted with either the ORIGIN PS or VANGUARD PS System will be included upon eligibility assessment. Subjects will be followed at one and two years after the procedure. The clinical assessment is presented in Chapter XXI APPENDICES.

Enrollment will occur at the time of the medical examination. It is assumed that the subjects' treatments and follow-up visits will be performed per standard of the investigational site in Germany.

It is anticipated that enrollment will take approximately 18 months. As each implanted subject is to be followed for two years, the estimated study duration is approximately 48 months, excluding the time required for preparing the final report. (A loss of approximately 10% is expected at the end of the study)

### B. Completion of the Clinical Investigation

The completion of a clinical investigation will coincide with the last visit of the last subject (supposed to be after 2 years follow-up visit):

- First patient in: JAN 2021
- Last patient in: JUNE 2022
- And when follow-up is complete for the clinical investigation, expected completion in JUNE 2024 (last patient last visit)
- Study closure: expected approximate date: OCT-2024

Except if the clinical investigation is terminated prematurely. (Cf. Chapter XVII EARLY TERMINATION OR SUSPENSION OF THE STUDY)

The Final Report will be prepared when all patients complete their follow-up evaluations. It will also be written after collected data are verified, cleaned, and after the eCRF is complete for data analysis.

### C. Randomization

There are three major identified barriers for randomized clinical trials on medical devices, namely: (1) randomization, including timing of assessment, acceptability, blinding, choice of the comparator group and considerations on the learning curve; (2) difficulties in determining appropriate outcomes; and (3)

SYMBIOS		 symbios  Clinical Investigation Plan	F029.03
Date	27.11.2019		Distribution Informatique pdf
Auteur	BGA		
Contrôle	EBO		
Libération	RAQ		

the lack of scientific advice, regulations and transparency. In order to build a powerful clinical study, randomization will be applied and patients will receive equal information regarding both prostheses treatment. The randomization procedure will be unpredictable so that investigators cannot guess the next subject's group assignment based on prior treatment assignments. The study will not be blinded, anyhow all attempt will be chosen to prevent bias regarding PROMs data collection and surgeon reported scores.

The study is a randomized trial with two arms:

- Arm 1/ Device under evaluation: Group of 70 subjects who will undergo a surgery with the ORIGIN PS System
- Arm 2/Comparative device: Group of 70 subjects who will undergo a surgery with the VANGUARD System Cf. CHAPTER. XXI. APPENDICES C. RANDOMIZATION FLOW CHART

The randomization will be performed via a secure unique comprehensive eHealth platform named Bepatient which will be used for the purpose of this study, as a live electronic case report form or eCRF. Additional data are displayed in Section XXI. APPENDICES. F. BEPATIENT DATA HANDLING

Bepatient eCRF ensures the respect of the compliance with good practices (21 CFR part 11) and in accordance with the General Data Protection Regulation (GDPR). Authorized site personnel as indicated on the Delegation Task List, will be trained on the use of the system and will be provided with a username and password to access the system in a limited and secure way. CRFs will be implemented to capture the data for each enrolled subject as required by the protocol.

The study methods include the following measures to minimize potential sources of bias:

- The enrolment is controlled and tracked in the eCRF (external partner) to avoid introduction of bias in the trial
- A dedicated Vigilance department will review all deaths and safety endpoint related adverse events
- The site will follow-up a standardized protocol for acquisition of endpoints data in the eCRF.
- Study site will ensure patients are well informed regarding both prosthesis treatment, to avoid introduction of bias in the questionnaire completion. Site will follow their own procedures regarding the execution of the study, in their facilities (eg. Radiological evaluation), involving nurses and clinical trial team in the clinical assessment, when appropriate to avoid bias of data collection.
- Study monitors will verify patients' data and ensure compliance with the Clinical Investigational Plan and other study requirements.

 <https://www.nweurope.eu/media/3231/specific-barriers-to-the-conduct-of-randomised-clinical-trials-on-medical-devices.pdf>

SYMBIOS		 symbios  Clinical Investigation Plan	F029.03
Date	27.11.2019		Distribution Informatique pdf
Auteur	BGA		
Contrôle	EBO		
Libération	RAQ		

## D. Investigational device(s) and comparator(s)

### a) Description of exposure to ORIGIN® & VANGUARD

ORIGIN® PS and VANGUARD® PS as compared total knee prostheses.

Name	ORIGIN® PS	VANGUARD® PS
Manufacturer	SYMBIOS Orthopédie SA	ZIMMER BIOMET
Type	Bi/tri compartmental	Bi/tri compartmental
Cinematic	Postero-stabilized	Postero-stabilized
Bearing	Fixed	Fixed
Femoral component		
Name	ORIGIN® PS Femur Cemented	Vanguard PS Closed Box Interlok stem
Material	CrCo	CrCo
Sizes	Patient-specific	10
Fixation	Cemented	Cemented
Tibial insert		
Name	ORIGIN® PS Insert	Vanguard PS Tib Bearing
Material	Standard polyethylene	Antioxidant polyethylene E1
Sizes	Patient-specific	5
Thickness	6 or 8 mm	10 to 24 mm (2 mm increments)
Tibial tray		
Name	ORIGIN® PS Tibia Cemented	CoCr Finned Tibial Tray
Material	Titanium	CrCo
Sizes	Patient-specific	9
Symmetry	Asymmetric	Symmetric
Fixation	Cemented	Cemented
Patellar component		
Name	ORIGIN Patella Cemented	Serie A Patella
Material	Polyethylene	Polyethylene
Instruments		
Cutting	KNEE-PLAN® Guides ORIGIN®	Conventional cutting guides
Other instruments	KNEE-PLAN® Set ORIGIN®	Standard instrumentation
Pre-operative planning		
Type	3D CT-Based with KNEE-PLAN®	2D X-rays 

According to regular clinical practice, x-rays (standing long leg, ap, lateral, patella sunrise views) are taken for all patients preoperatively as well as a planning CT-scan of hip, knee and ankle for patients randomized to the Origin group.

 Long leg, knee in 2 planes and patella sunrise

SYMBIOS		 symbios  Clinical Investigation Plan	F029.03
Date	27.11.2019		Distribution Informatique pdf
Auteur	BGA		
Contrôle	EBO		
Libération	RAQ		

*b) Discussion of implant's risks, pros and cons*

Standard TKA implants are off-the-shelf and therefore only come in a certain number and range of sizes. Manufacturers aim to provide solutions for most patients with a limited number of implants. Essential interindividual differences have been shown to exist regarding the size of the femoral condyles, trochlear morphology and geometry of the tibial plateau (Steiner AF et al. Orthopade 2016). To accommodate for a patient's individual anatomy, a surgeon must therefore find the best fit option for each patient which when using OTS implants in some cases means to compromise between implant rotation, fit and bony coverage. Since femoral overhang and tibial malrotation have been linked with persistent postoperative pain (Mahoney OM et al. J Bone Joint Surg 2010; Nicoll D et al. J Bone Joint Surg Br 2010) these compromises might lead to dissatisfaction after TKA surgery. With a custom implant recreating a patient's individual anatomy said compromises shouldn't be necessary anymore, possibly resulting in a higher patient satisfaction.

While younger, more active patients profit from more normal kinematics as outlined in the introduction, custom implants hold potential benefits for elderly patients as well. Osteoporotic bone is a common problem in this age cohort and to avoid subsidence surgeon's aim for cortical coverage of the tibial base plate. While this can easily be achieved with a CIM TKA, the same is difficult and sometimes impossible with OTS TKA.

While the individuality of CIM implants leads to the upsides mentioned above, the manufacturing process of individual knee implants is inherently different from the one of OTS implants. A CT scan needs to be done to compute a 3D model of a patient's knee according to which the final implants will be produced within a 6 to 8 week timeframe. One might argue this waiting period is to a disadvantage for patients randomized into the CIM TKA group, but in our experience the waiting period for this type of elective orthopedic surgery is approximately 6 to 8 weeks anyways.

Another possible downside of CIM implants arises in the case of an early periprosthetic infection. Following the DAIR (debridement, antibiotics and implant retention) approach, inserts should be exchanged during revision surgery. While new inserts for OTS implants are usually on stock, this might not be the case for CIM inserts. From our point of view this can be handled by requesting a replacement insert from the manufacturer. If the patient needs emergency surgery, leftover inserts kept from his primary surgery can be used until this replacement is available.

## E. Study population

The study population includes patients suffering from non-inflammatory degenerative and inflammatory knee joint disease and for who no alternative treatments are possible.

It anyhow includes patients who have provided consent to participate in the study. Patients who have met the protocol eligibility criteria will be enrolled into the prospective study.

Pediatric, legally incompetent, or otherwise vulnerable patients are not eligible for the study.

SYMBIOS		 symbios  Clinical Investigation Plan	F029.03
Date	27.11.2019		Distribution Informatique pdf
Auteur	BGA		
Contrôle	EBO		
Libération	RAQ		

## F. Inclusion criteria

It is planned to include consecutive eligible subjects which will be randomized to Arm 1: ORIGIN SYSTEM or Arm 2: VANGUARD system. Subjects will be enrolled upon evaluation via a clinical examination at the preoperative stage. Subjects should meet the following criteria:

- Male and female over 18 years of age.
- Each patient, or his or her guardian or legal representative, is willing to give informed consent.
- Clinically indicated for a total Knee replacement
- Females who are not pregnant or lactating and not planning to become pregnant  $\leq 12$  months. A pregnancy test may be performed to confirm this
- Geographically stable and willing to return to the implanting site for all follow-up visits.

## G. Exclusion criteria

Patients meeting any one of the following criteria will be excluded from participating in this study:

- Life expectancy  $\leq 1$  year
- Age  $\geq 80$  years
- Acute or chronic, local or systemic infection
- Mental illness
- Muscular, ligamental, neurological, psychological or vascular deficits
- Bone destruction or poor bone quality likely to affect implant stability (requiring a femoral and/or a tibial stem and/or a thick insert)
- Any concomitant condition likely to affect implant integration or function
- Allergy or hypersensitivity to any of the materials used
- For devices in CoCrMo (ISO 5832/4): renal and hepatic impairment
- Hip Knee Ankle (HKA) angle  $< 165^\circ$  or  $> 195^\circ$
- Severe collateral ligaments deficiency (requiring a more constrained prosthesis)
- Major anatomical deformities
- Severe flexion contracture or severe recurvatum
- Revision of a partial or total knee prosthesis
- Non-extractible material (e.g. screws, plate, intramedullary nail, osteosynthesis material...) which can create a conflict with any component of the prosthesis
- Distal and/or posterior and/or anterior femoral bone loss which exceeds the femoral component thickness
- Proximal tibial bone loss which exceeds the tibial component thickness (tibial tray + tibial insert)
- Allergy of any implant material

## H. Criteria and procedures of subject withdrawal or lost to follow-up

SYMBIOS		 symbios  Clinical Investigation Plan	F029.03
Date	27.11.2019		Distribution Informatique pdf
Auteur	BGA		
Contrôle	EBO		
Libération	RAQ		

*a) Missed Follow-up Visit*

The Investigator should make every effort to contact the subject preferably within the visit window, to collect the subject’s vital status as well as information related to potential adverse events, safety data, and hospitalizations.

As only standard of care data are being collected, subjects cannot miss study-specific visits. In case no standard of care visit has taken place in the pre-specified follow-up interval period, sites should conduct a telephone follow-up visit just prior to the closure of the visit window. Up to 2 attempts and any information received during a telephone follow-up should be filed as source documentation by the sites. If the subject cannot be reached by phone, the visit should be considered missed and, if applicable a protocol deviation must be completed, as outlined in chapter XII. DEVIATION FROM THE CLINICAL INVESTIGATION PLAN.

A replacement of withdrawn or discontinued subjects in the study is not planned. Therefore, these subjects will be documented as lost-to-follow-up in the source documentation.

*b) Lost to Follow-Up*

The subject may only be considered lost to follow-up after all efforts to obtain compliance are exhausted. At a minimum, three attempts must be made to contact the subject and documented in the subject’s trial records:

- 2 telephone attempts to the subject’s last known phone number, and if unsuccessful,
- 1 certified letter from the PI to the subject’s last known address

If the site is unable to reach the subject after the documented attempts, the site should make every attempt to verify the subject’s vital status (alive or deceased). Should the participant continue to be unreachable, he or she will be considered to have withdrawn from the study with a primary reason of lost to follow-up.

*c) Subject Withdrawal*

All subjects will be encouraged to remain in the study through the last follow-up visit at two years. Subjects who discontinue participation prematurely will be included in the analysis of results (as appropriate) but they will not be replaced in the enrollment of total study subjects. If a study subject is discontinued from the study early, the reason for discontinuation should be documented in the subject file and a Study Exit e-CRF must be completed. If discontinuation is because of safety or lack of effectiveness, the patient shall be asked to be followed for collecting safety data outside the clinical study.

Once a subject has been enrolled in the study (i.e. written Informed Consent has been obtained) he/she may withdraw his/her consent to participate in the study at any time without prejudice. Participation in this study is entirely voluntary.

If a subject discontinues the study at any time, is withdrawn from the study early, or completes all follow-up visits they should continue to be followed by the implanting center according to their standard clinical practice.

SYMBIOS		 symbios  Clinical Investigation Plan	F029.03
Date	27.11.2019		Distribution Informatique pdf
Auteur	BGA		
Contrôle	EBO		
Libération	RAQ		

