Study endpoints:	
 
• Primary endpoint: 
 
○ To compare the ability of patients to forget their operated knee at 1 year after the surgery, measured by the Forgotten Joint Score 12 (FJS-12 Knee). The goal is to assess patient satisfaction regarding the surgery with a CE marked custom-made implant (ORIGIN®) versus off-the-shelf (VANGUARD PS) device with a self-administrated patient satisfaction questionnaire.
 
 
 
• Secondary endpoints: 
 
○ Evaluate the success of the procedure
 
○ Evaluate outcomes & complications & revision rate with the ORIGIN SYSTEM versus VANGUARD PS at the last (2y) follow-up visit
 
○ Evaluate performance of the ORIGIN System vs VANGUARD PS at 2 years follow-up: clinical examination and scoring. To evaluate/compare the clinical, functional and quality of life outcomes using the following scores: 
 
○ The Knee Injury and Osteoarthritis Outcome Score (KOOS)
 
○ The Oxford Knee Score (OKS)
 
○ The EQ-5D-5L Score
 
○ A self-administrated patient satisfaction questionnaire.
 
 
 
○ Evaluate the radiographic limb alignment, radiolucent lines and radiographic loosening (according to the “Modern Knee Society Radiographic Evaluation System and Methodology for Total Knee Arthroplasty” version 2015)
 
○ To evaluate/compare the radiological results (measurements and observations by surgeon reported scores: 
 
○ The Knee Society Score (KSS) (Objective Knee Indicators only)
 
○ Knee Society Radiographic Evaluation and Scoring System (KSRESS)
 
○ The Single Leg Stance Test (SLS)
 
○ The Timed Up & Go test (TUG)
 
 
 
 
 

N sites	1 – UMC MAINZ
Sample size	140  However, enrollment will occur at the time of the medical examination. It is assumed that the subjects’ treatments and follow-up visits will be performed per standard of care in the participating site
Total study duration:	48 months  
 
- Start- up phase: 3 months
 
- Enrolment: 18 months
 
- Follow-up phase: 24 months
 
- Study closure: 3 months
 

SYMBIOS		 symbios  Clinical Investigation Plan	F029.03

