### B. Clinical endpoints

#### a) *Primary endpoints*

- The hypothesis regarding the scoring is that patients receiving ORIGIN implants will experience a more natural feel of the prosthesis during the first year after the surgery compared to patients receiving VANGUARD implants (as measured with FJS)
- The primary endpoint of this study is:

SYMBIOS		 symbios  Clinical Investigation Plan	F029.03
Date	27.11.2019		Distribution Informatique pdf
Auteur	BGA		
Contrôle	EBO		
Libération	RAQ		

- To compare the ability of patients to forget their operated knee at 1 year after the surgery, measured by the Forgotten Joint Score 12 (FJS-12 Knee).
- To compare patient satisfaction regarding the surgery with a CE marked custom-made implant (ORIGIN®) versus off-the-shelf (VANGUARD PS) device. A short self-reported questionnaire will be used.

*b) Secondary endpoints will evaluate clinical performance and safety of ORIGIN System:*

- **Secondary endpoints:**

- Evaluate the success of the procedure
- Evaluate surgeon satisfaction regarding the use of implants and instruments
- Evaluate outcomes: complications & revision rate with the ORIGIN SYSTEM at the last (2y) follow-up visit
- To compare the PROMs between the two groups at 1y follow-up and 2y follow-up visits.
- Evaluate performance of the ORIGIN System vs VANGUARD PS at 2 years follow-up: clinical examination and scoring.
- To evaluate/compare the clinical, functional and quality of life outcomes using the following four scores:
  - Clinical examination
  - The Knee Injury and Osteoarthritis Outcome Score (KOOS)
  - The Oxford Knee Score (OKS)
  - The EQ-5D-5L Score
  - A self-administrated patient satisfaction questionnaire.
- To evaluate/compare the clinical, functional and quality of life outcomes with the following surgeon reported scores:
  - The Knee Society Score (KSS) (Objective Knee Indicators only)
  - Knee Society Radiographic Evaluation and Scoring System (KSRESS)
  - The Single Leg Stance Test (SLS)
  - The Timed Up & Go test (TUG)
- Radiological evaluation:
  - X-rays: AP, lateral, sunrise, long leg weight bearing film
  - Femoral patellar arthrosis: Iwano classification (stage 1 mild to 4 very severe),
  - KRESS Radiological assessment: Patellar tilt angle, patellar displacement, tibial slope, anatomical axis (angles  $\alpha - \beta$ ), mechanical axis, (HKA angle, F angle, T angle, HKS angle)

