#### *c) Analysis of clinical data and Safety outcomes*

The rate of serious adverse events (SAE) and Unanticipated Adverse Device Effects (UADEs) during the study will be presented using the proportions of patients experiencing one or more of each SAE and UADE. All serious and non-serious adverse events will be characterized in terms of severity and relatedness to the operative procedure and device. Additionally, the percent of patients requiring one or more secondary surgical procedures relating to the original procedure will be presented. Data will be analyzed for all patients enrolled in this observational study.

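### Revisions and complications after an exit for safety or lack of effectiveness have no stated route into the 2-year endpoint

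*Combined protocol and SAP*

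**What the plan says.** **Exit rule.** Section VII.H.c encourages all subjects to stay to the 2-year visit. A subject who leaves early has a Study Exit form completed. If the reason is safety or lack of effectiveness, "the patient shall be asked to be followed for collecting safety data outside the clinical study". For anyone who leaves or completes, "they should continue to be followed by the implanting center according to their standard clinical practice". Neither sentence says that what is learned there goes into the study database.

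**Labelling.** Section VII.H.a says of withdrawn or discontinued subjects that "these subjects will be documented as lost-to-follow-up in the source documentation". Section VII.H.b keeps that label for people who cannot be reached after two telephone attempts and a certified letter.

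**Endpoint.** The Synopsis lists complications and "revision rate with the ORIGIN SYSTEM versus VANGUARD PS at the last (2y) follow-up visit" as secondary. Section VI.B.b has "Evaluate outcomes: complications & revision rate with the ORIGIN SYSTEM at the last (2y) follow-up visit". Section VIII.F.d evaluates revisions in both arms at 2 years, with an adverse event form for each.

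**Capture while in the study.** Section VI.D, repeated in XVI.H, says "The following list of safety outcomes should be collected in the eCRF case report form"; the list includes revisions and secondary procedures.

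**Analysis.** Three statements bear on who is counted:
- VII.H.c: "Subjects who discontinue participation prematurely will be included in the analysis of results (as appropriate"). The closing qualifier is not defined.
- X.c: "the percent of patients requiring one or more secondary surgical procedures relating to the original procedure will be presented", with data analysed for every enrolled patient.
- X.e: no imputation, and a subject with missing data is left out of the analysis concerned.

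**The concern.** The treatment is a permanent implant, so leaving the study does not end exposure to it. Section VII.J says each implanted subject is to be followed for two years. The rule in VII.H.c applies to exits for safety or lack of effectiveness, the group in which later revisions and complications are most to be expected. It is the one group for which the plan says that further safety data are gathered elsewhere.

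The trial is not blinded (VII.C), so leaving for perceived lack of effectiveness could differ between arms. The comparison of revision and complication rates could then be distorted, as well as their level. Sections VIII.F.c and VIII.F.d look for a revision rate no higher than the state of the art, and IV.D sends the results to the clinical evaluation and post-market surveillance reports. An undercount pushes towards the favourable conclusion.

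**Working it through.** **1. The plan's own figure.** The only sample size is for FJS (X.a): n = 2/ES² × (1.96 + 0.84)², with ES = 13.4/26.8 = 0.5. This gives 8 × 7.84 = 62.72, so 63 per group; adding 7 for 10% loss gives 70. The figure reproduces and this point does not alter it. The plan gives no figure for revision at 2 years.

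**2. Following one subject through the text.** Take a subject who exits for lack of effectiveness and is revised later but before 2 years.
- VI.D and XVI.H: eCRF capture covers what happens while the subject is in the study, including an event that prompts the exit.
- VII.H.c: after exit, safety data are gathered beyond the study, and only if the subject agrees.
- X.c and X.e: neither adds events found elsewhere.

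The later revision is therefore not counted.

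**3. Direction under each denominator.** Let an arm have 70 subjects, e such exits, 2-year revision risk r among those who stay and risk q after exit. For simplicity, assume no revision before exit among the e.
- Later events counted: [(70 − e)r + eq]/70
- Not counted, exited subjects kept (X.c): (70 − e)r/70, too low whenever q > 0
- Not counted, exited subjects omitted (X.e): r, too low whenever q > r

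Neither rule recovers the event. The undercount under omission needs q to exceed r, which is plausible for exits chosen on poor outcome but is an assumption.

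**4. Size, for illustration only.** The documents give neither e nor q. For r, 2% is borrowed from VI.A.b, where it is a 1-year claim from the clinical evaluation and not a 2-year expectation for this trial. It corresponds to 0.02 × 70 = 1.4 revisions per arm. One uncounted revision is 1/70 = 1.4 percentage points.

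| e of 70 | q | Later events counted | Not counted, kept | Not counted, omitted |
|---|---|---|---|---|
| 1 | 10% | (1.38 + 0.10)/70 = 2.1% | 2.0% | 2.0% |
| 1 | 25% | (1.38 + 0.25)/70 = 2.3% | 2.0% | 2.0% |
| 2 | 25% | (1.36 + 0.50)/70 = 2.7% | 1.9% | 2.0% |
| 3 | 50% | (1.34 + 1.50)/70 = 4.1% | 1.9% | 2.0% |
| 7 | 10% | (1.26 + 0.70)/70 = 2.8% | 1.8% | 2.0% |
| 7 | 50% | (1.26 + 3.50)/70 = 6.8% | 1.8% | 2.0% |

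The rows with e = 7 treat the whole 10% loss allowance as exits of this kind, which is an upper extreme. Without the later events the rate reads 1.8% to 2.0% throughout.

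**5. Against sampling error.** Exact 95% intervals are 0.04% to 7.7% for 1/70 and 0.3% to 9.9% for 2/70. One lost event lies well within chance variation, but the omission acts in one direction and the interval does not reflect it.

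**The case against.** The case on the other side is substantial.

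- **No exit criterion.** A reader might infer that VII.H.c makes poor function or a safety problem a reason to leave. It does not. The sentence is conditional and deals with someone who has already stopped. Nothing in VII.H ends participation because of pain, stiffness or revision, and X.e's exclusion of subjects with further procedures in the first six months is from an analysis, not from the study. This stands, so the number of affected subjects may be small.
- **Earlier events are captured.** Revisions and complications before exit, or prompting it, go into the eCRF. This stands; only later events are exposed.
- **Denominator.** A reader might infer from X.c that exited subjects always count as event-free. X.e points the other way, and the plan does not choose. This stands as a limit on the mechanism, but neither rule restores the missing event.
- **FJS.** A reader might also infer that the rule inflates mean FJS by some definite amount. The quoted sentence concerns safety data only. Loss of FJS follows from the missing-data rule in X.e, and the documents give no number or scores for such exits, so no amount can be derived.
- **Consent and unseen documents.** Section XV lets subjects withdraw consent, have data erased and object to its use, and asking someone who has left for safety data elsewhere is a reasonable courtesy. The SAP announced in X.e was not available and may define the denominator. It cannot analyse data that the protocol leaves out of the database. Consent limits the remedy but does not remove the need for it.
- **Secondary and unpowered.** X.e says the study was not powered for revision rates. This stands and limits the weight of the point.

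**Conclusion.** The point holds in a limited form. As written, the plan leaves uncounted any revision or complication that follows an exit for safety or lack of effectiveness, in a group selected on outcome and in an unblinded trial. The 2-year rate is biased low under the denominator of X.c if any such event occurs, and under the omission rule of X.e if these subjects have a higher later risk than those who stay.

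The actual size cannot be derived, because the number of exits and their later risk are not in the documents. What can be said is that each uncounted revision is worth 1.4 percentage points in an arm of 70; the table shows how that accumulates under assumed inputs. The documents do not support reading the point as systematic removal of the worst-outcome patients, or as a quantified effect on FJS. The primary sample size is unaffected. Sections VII.H.c, X.c and X.e need to be reconciled with one another, as do VII.H.a and VII.H.b on labelling.

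**What to change.** 1. In VII.H.c, delete the closing words that place safety follow-up beyond the study, and distinguish stopping study visits from stopping data collection.
2. Unless the subject withdraws consent to data use (XV), record revision and complication status, with dates, in the study eCRF to 2 years. The source can be the implanting centre's standard-practice follow-up, which VII.H.c already expects. Collect FJS-12 at 1 and 2 years where the subject agrees.
3. In VII.H.a, do not label discontinued subjects as lost to follow-up while they can be reached; keep that label for the situation defined in VII.H.b.
4. In X.c and X.e, state one denominator for the revision percentage, define the qualifier in VII.H.c to match it, and report by arm how many subjects have unknown 2-year status.

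The cost is a revised paragraph in VII.H.c with short edits to VII.H.a and X, an option on the Study Exit form for visits stopped with data follow-up continuing, and a line in the patient information about continued record follow-up. The protocol change needs ethics committee approval. No subject is added, and clinical care does not change.
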